Section 9.2 Sample size determination	A clarification was added that the primary-endpoint assessment will include all patients from Part 1 and Part 2. A combined total of approximately 98 patients are planned to be randomized in both parts. The relative contribution of Part 1 and Part 2 to the combined total may vary.	The number of participants in Part 1 could deviate from the planned target of 18. As the statistical analysis will be done on the combined total of participants in Part 1 and 2, sample size calculations were not done separately for either subpart.	
Section 9.4.6 Other Analysis	Change in urinary albumin/creatinine ratio (UACR) was deleted from the protocol.	UACR assessment, from the group of "other" endpoints, was deleted to reduce patient burden as it was considered as non-essential for the objective of this study in NPDR patients.	

09 FEB 2023 Page: 89 of 95

Section # and Name	Description of Change	Brief Rationale
	of treatment with top-line efficacy and safety results over both parts.	Since the duration of the study has been shortened to 48 weeks, the Week 48 analysis will be the final analysis, rather than the previously planned interim analysis.

Organizational changes, corrections, and clarifications

Section # and Name	Description of Change	Brief Rationale
Throughout	Description of the protocol package has been deleted, together with mentions to referring to Study Part B, Part B Study protocol, and Master protocol.	As of this amendment, Part B of the study has been removed. Late stage clinical development is not planned to be pursued with runcaciguat but with other sGC-activator(s).
		Former Part A now corresponds to the study as a whole. Therefore, for ease of readability, all applicable sections of Master protocol have been transferred to the current protocol. All mentions of Part B and Master protocol have been removed throughout the document.
Terminology throughout the document	Part A.1 renamed Part 1, Part A.2 renamed Part 2.	With the deletion of Part B from the protocol, the term "Part A" was eliminated.
Section 1.3 Schedule of activities (SoA)	Dispensation of urine pregnancy test at Visits 13 and 14 was added.	Added as separate activity after deletion of on-site pregnancy test.
Section 4.1.1 Part 1 – PK/PD	Text changed to reflect the changes to the Schedule of Activities.	Alignment with changes to schedule of activities. For details see changes to Section 1.3, above.
Section 4.2 Scientific rationale for study design	Mention of CONCORD data in addition to previously performed Phase 1 studies	Available masked CONCORD data support the planned use of runcaciguat in the NEON-NPDR study
Section 4.3 Justification for dose	Reference to masked CONCORD data added and discussed in the context of dose-justification and titration regimen	The titration scheme in the NEON-NPDR is the same as in the CONCORD study. This titration scheme was well tolerated.
Section 5 Study population	A clarification was added that participants should show typical fundus alterations as described in the DRSS criteria for moderately severe and severe NPDR without DME in need of treatment and no previous experience of anti-VEGF treatment.	To depict better the study population.
Section 5.6 Selection of the study eye	Preference for choosing the eye without any sign of DME as study eye added.	To minimize risk of intermittent requirement of DME treatment.

09 FEB 2023 Page: 90 of 95

Section #	Description of Change	Brief Rationale	
Section 6.3 Measures to reduce bias	Re-dispensing of unopened and undamaged bottles to the same participant allowed. Sentence moved to section 6.4.	To avoid wasting of clinical trial supplies. Section 6.4 more appropriate.	
Section 6.8 Concomitant Therapy	sGC stimulator vericiguat added to list of prohibited medications.	Vericiguat obtained marketing approval.	
Section 8.1.1 Ophthalmology assessments	Further clarification on archiving ophthalmology data on the site was provided.	Clarification	
Section 8.1.1.3 Fluorescein angiography	All FA images will be archived. The method of archiving was deleted.	Method of archiving left to the discretion of the investigational site.	
Section 8.1.1.4 OCT	A reference was added to specify the use of CRT measured by central reading Centre in the context of the amended EC6.	Change necessary in the context of the amendment of EC 6.	
Section 8.2.1 Physical examination	Clarification that height is measured only at screening was added.	Clarification	
Section 8.2.3 Electrocardiograms	The resting time before ECG recordings was reduced from 10 to 5 minutes.	The resting time was aligned throughout the protocol and with vital sign assessments. The 5-minute resting period is deemed sufficient for the purpose of ECG-assessments in this study.	
Section 8.2.4 Clinical safety laboratory assessments Section 10.2. Appendix 2: Clinical laboratory tests	eGFR calculation to be done by the central laboratory. Paragraph on eGFR calculation deleted from Section 10.2 as unnecessary.	eGFR to be determined by central laboratory to allow real-time reporting of results which are used as a stopping criterion.	
Section 8.4 Pharmacokinetics	Duration of PK sampling only until Visit 12. Snap-shot interim analysis deleted. PK data will first be assessed at the 24-week interim analysis.	Aligned with reduced treatment duration. Aligned with new plans for interim analyses.	
Section 8.4 Pharmacokinetics	Sentence "Non-compartmental PK parameters will not be evaluated in this study" was deleted.	The sentence was deleted to allow greater flexibility and the possibility of exploratory analyses.	
Section 9.5 Interim analysis	Interim analysis will be after 24 weeks of treatment with top-line efficacy and safety results over both parts. Interim analysis for Part 1 restricted to week 24 only.	Since the duration of the study has been shortened to 48 weeks, the Week 48 analysis will be the final analysis, rather than the previously planned interim analysis.	
Section 10.2 Appendix 2: Clinical laboratory tests	Two paragraphs explaining the possibility to perform additional laboratory tests were deleted as they were redundant with a third paragraph that remains.	Deletion to avoid redundant text. Redundant with paragraph in protocol Section 8.2.4	

09 FEB 2023 Page: 91 of 95

In addition, minor editorial and formatting revisions, including clarifications of existing text, have been made throughout the document.

10.8.3 Amendment 2

Amendment 2 (13 JAN 2021)

This amendment is considered to be substantial based on the criteria set forth in Article 10(a) of Directive 2001/20/EC of the European Parliament and the Council of the European Union.

Overall rationale for the amendment:

This amendment was implemented to accommodate requests by Competent Authorities and Independent Ethics Committees on the use of the smartphone app to support drug adherence. In addition, endpoint assessments were specified and additional endpoints included.

A description of changes applicable to protocol part A and a brief rationale is outlined in the table below.

Section # and Name	Description of Change	Brief Rationale
Table 1-5 Section 8.2.3 Electrocardiograms	Triplicate ECGs only recorded up to study Visit 6 (inclusive) of Part A.1	Triplicate ECG recordings to be done throughout the titration period only to support analyses of QT-time relative to exposure on visit days with extended duration.
Section 6.4 Study intervention compliance	Use of the smartphone app for supporting and tracking participant adherence to study drug intake was changed to be optional.	Competent Authority and Ethics Committee request
Section 8.1.1.1 Color fundus photography (CFP)	Additional exploratory efficacy endpoints based on color fundus photographs were added.	Potential additional explorative assessments to be disclosed.
Section 8.1.1.5 Optical coherence tomography angiography (OCT-A)	The experimental nature of the software used to assess cross -sectional macular full depth line scans was indicated.	It was deemed appropriate to highlight the experimental nature of this OCT-A based image acquisition.

In addition, minor editorial and formatting revisions have been made throughout the document

10.8.4 Amendment 1

Amendment 1 (23 NOV 2020)

This amendment is considered to be substantial based on the criteria set forth in Article 10(a) of Directive 2001/20/EC of the European Parliament and the Council of the European Union.

09 FEB 2023 Page: 92 of 95

Overall rationale for the amendment:

This amendment was implemented to follow requests from the Bundesinstitut für Arzneimittel und Medizinprodukte (BfArM) and central Independent Ethics Committee (IEC). A description of changes applicable to protocol Part A and a brief rationale is outlined in the table below.

Section # and Name	Description of Change	Brief Rationale
Section 4.1.1 Part A1 – Run in	Decisions made by safety assessment group will be reviewed by DMC.	Health authority request
Section 10.1.5.4 Safety assessment group		
Section 5.2 Exclusion criteria	Exclusion criterion 27 has been modified to include time period for prohibited medication	Health authority request
Section 5.2 Exclusion criteria	Exclusion criteria 28 and 29 have been modified to prohibit the use of nitrates, NO donors, PDE5 inhibitors, non-specific PDE inhibitors and sGC stimulators within 1 week or less than 5 half-lives (whichever is longer) before first study drug administration	Health authority request
Section 6.5.1 Intra- individual dose-titration decisions	Investigator should reduce the dose instead of maintaining it in cases of serious or severe AEs related to runcaciguat, or in cases of relevant hypotension (e.g. symptoms of hypotension in combination with either SBP < 90 mmHg or SBP decrease by >30 mmHg or both)	Health authority request
Section 6.5.2 Stopping rules (study level)	Safety findings observed by DMC which preclude indicate unacceptable pharmacological effects, reasonably attributable to runcaciguat [result in an immediate stop of dosing and will result in a temporary halt of the study]	Correction of obvious mistake
Section 7.1.1 Permanent discontinuation	Modification of discontinuation criteria: participants must be withdrawn from study intervention on all cases of repeated incidents of relevant hypotension or tachycardia, and in cases of safety concerns for a participant by the investigator or the sponsor	Health authority request
Section 8.1.2 Vision threatening complications	Treatment of the vision threatening complication should follow local standards and guidelines.	Health authority scientific advice recommendation
Section 8.2.5 Pregnancy testing	Urine pregnancy testing was corrected to be done locally, serum pregnancy test is done centrally.	Non-substantial correction

09 FEB 2023 Page: 93 of 95

Section # and Name	Description of Change	Brief Rationale
Section 8.5 Genetics Section 8.6 Biomarkers	More detailed description of the genetic testing was included	Ethics Committee request
Section 10.1.5.4 Safety assessment group	Addition that the decision by the safety assessment group will be reviewed by the DMC based on an unmasked safety review.	Health authority request
Section 10.1.5.1 Central reading centers	The digital retinal images OCT scans, fluorescence angiographies, and ECG print-outs will be assessed by independent central reading centers	Correction of obvious mistake in protocol as to examinations to be provided to central reading centers, in accordance with existing language in protocol Sections 8.1.1.1, 8.1.1.3, 8.1.1.4, 8.1.1.5.
Section 10.2 Appendix 2: Clinical laboratory tests	Missing serum pregnancy test was added	Non-substantial correction

In addition, minor editorial and formatting revisions have been made throughout the document.

11. References

- AREDS. The Age-Related Eye Disease Study (AREDS): design implications. AREDS report no. 1. Control Clin Trials. 1999 Dec;20(6):573-600.

## **Version History**

This Statistical Analysis Plan (SAP) for study 20739 is based on the clinical study protocol (CSP) (Version 5.0, Amendment number 4, dated 09 FEB 2023).

SAP Versio	Date n	Section	Change	Rationale
1.0	31 AUG 2023	Not applicable	Not applicable	Original version
2.0	17 NOV 2023	1.1 Objectives and Endpoints 4.2.2 Main Analytical Approach	The estimands framework was added for objectives and endpoints related to the DRSS.	To make the best use of all available r data, including data from participants who discontinue the study early, the estimands framework was applied to the DRSS endpoints
		4.3.1 Secondary Endpoints	The scale for DRSS across both eyes was changed to the for persons scale and the analysis was adapted accordingly.	Based on feedback from HAs the primary endpoint for Phase III studies in NPDR will be the DRSS for persons scale (see Section 6.6). Accordingly, the DRSS endpoints across both eyes was adapted to gain insights and allow comparability.
		1.1 Objectives and Endpoints 4.6.3 Biomarkers Further sections	The list of biomarker endpoints was adapted, and more comprehensive analyses of biomarkers were added. Other minor corrections (e.g., typos) not affecting the final analysis.	The study team decided to include the analysis of biomarkers within the CSR, and not write a separate BER. Furthermore, see Section 4.8.
3.0	03 MAY 2024	4.3.2 Subgroup Analyses	Definition of an additiona subgroup	An improvement from PDR to NPDR is extremely unlikely. The subgroup was defined to only include participants without PDR at baseline.
		Further sections	Minor corrections and additions	

## List of Abbreviations and Definitions of Terms

ACIR	Assessment criteria and identification requirements
AE(s)	Adverse event(s)
AESI(s)	Adverse event(s) of special interest
ALT	Alanine aminotransferase
AST	Aspartate aminotransferase
BCVA	Best corrected visual acuity
BM	Biomarker
BMI	Body mass index
CEC	Clinical endpoint committee
CFP	Color fundus photography
CI	Confidence interval
CKD-EPI	Chronic Kidney Disease Epidemiology Collaboration
COVID-19	Coronavirus disease of 2019
CRF	Case report form
CRT	Central retinal thickness
CSP	Clinical study protocol
CV	Coefficient of variation
DBP	Diastolic blood pressure
DMC	Data Monitoring Committee
DME	Diabetic macular edema
dpt	Diopter
DR	Diabetic retinopathy
DRSS	Diabetic Retinopathy Severity Scale
EC	Ethics committee
ECG(s)	Electrocardiogram(s)
eCRF	Electronic case report form
(e)GFR	(Estimated) glomerular filtration rate
EoS	End of study
ЕоТ	End of treatment
ETDRS	Early Treatment Diabetic Retinopathy Study
FA	Fluorescein angiography
FAS	Full analysis set
HbA1c	Hemoglobin A1c (glycated hemoglobin)
HDL	High density lipoprotein
HLGT	High-level group term
ICF	Informed consent form
INR	International normalized ratio

# Statistical Analysis Plan BAY 1101042 / 20739 Version 3.0

IQR	Interquartile range
IRB	Institutional review board
LDL	Low density lipoprotein
LLOQ	Lower limit of quantification
LOCF	Last observation carried forward
MedDRA	Medical dictionary for regulatory activities
MH	Medical history
NPDR	Non-proliferative diabetic retinopathy
OCT	Optical coherence tomography
OCT-A	Optical coherence tomography angiography
PD	Pharmacodynamics
PDR	Proliferative diabetic retinopathy
РК	Pharmacokinetics
PKS	Pharmacokinetic analysis set
PoC	Proof-of concept
Pop-PK	Population pharmacokinetics
PPS	Per protocol set
РТ	Preferred term
QD	Quaque die, daily
SAC	Statistical analysis center
SAE(s)	Serious adverse event(s)
SAF	Safety analysis set
SAP	Statistical Analysis Plan
SAS	Statistical analysis system
SBP	Systolic blood pressure
SCr	Serum creatinine
SD	Standard deviation
sGC	Soluble guanylyl cyclase
SoA	Schedule of activities
SOC	System organ class
TEAE(s)	Treatment emergent adverse event(s)
TLF specification	Table, listing and figure specification
ULN	Upper limit of normal
ULOQ	Upper limit of quantification
VTC	Vision threatening complications
WHO-DD	World Health Organization Drug Dictionary

#### 1. Introduction

Runcaciguat (BAY 1101042) is a sGC activator that improved function and retinal structure in pre-clinical DR models.

This PoC study includes a subpart with PK/PD assessments (Part 1). Part 1 enrolls a subset of patients at a more intense investigation in specific study sites. Part 2 is the main PoC part, to be conducted in ophthalmology sites, that enrolls the majority of participants. PoC will be based on the evaluation of outcomes in participants from both parts, which will be running in parallel.

The present study is to be conducted to obtain information on sGC activators by investigating

1. whether runcaciguat improves the diabetic retinopathy score in patients with moderately severe to severe NPDR

and to

2. explore the PK/PD relationship of runcaciguat on retinal perfusion

This SAP describes the final analysis of the study. No statistical interim analysis will be performed. TLF specifications are contained in a separate document. The analysis of Pop-PK data will not be described here but will be done in a separate analysis plan.

## 1.1 **Objectives and Endpoints**

The objectives and endpoints are summarized in Table 1-1.

#### Table 1-1: Study objectives and endpoints

Objectives	Endpoints
Primary objective: Efficacy Establish the PoC for the efficacy of the sGC activator runcaciguat in the treatment	
 
Primary endpoint:
 
DRSS improvement ≥ 2 steps at 48 weeks of treatment in the study eye
 

of NPDR.	
 
Secondary endpoints for primary objective:
 
VTC at 48 weeks of treatment in the study eye
 
DRSS improvement ≥ 2 steps at 24 weeks of treatment in the study eye
 
DRSS improvement ≥ 3 steps at 48 weeks of treatment on the scale for persons
 

	
 
Other endpoints (for primary objective):
 
DRSS worsening of ≥ 3 steps at 48 weeks of treatment in the study eye
 
Change in visual acuity from baseline
 
Change in leakage area on FA
 
DRSS changes from baseline in the study and fellow eye
 
VTC in any eye up to 48 weeks of treatment
 

Secondary objective: Safety Investigate the safety and tolerability of runcaciguat in patients with NPDR	
 
Secondary endpoints for secondary objective:
 
Frequency of TEAEs
 
Other endpoints (for secondary objective): 
 
Laboratory parameters
 
Vital signs
 
 
 

Other objectives Characterize PD effects of runcaciguat in patients with NPDR	
 
Electrocardiography
 
Other endpoints 
 
Central retinal thickness
 
HbA1c
 
Other biomarkers
 
 
 

Characterize PK of runcaciguat in patients with NPDR	
 
Pop-PK
 
Pre-dose (trough) plasma concentrations of runcaciguat by visit
 

Further investigate the study intervention and similar drugs (e.g., mode-of-action related effects, safety) and to further investigate pathomechanisms deemed relevant to NPDR, (cardio)vascular diseases and associated health problems	Various biomarkers (e.g., diagnostic, safety, PD, monitoring, or potentially predictive biomarkers)

Version 3.0

#### The primary estimand (analysis on PPS) is defined below:

#### Estimand label: primary

#### **Endpoint:**

All DRSS derived efficacy endpoints

#### **Population:**

Adult patients with

- moderately severe to severe NPDR in the study eye (DRSS levels 47 or 53)
- Diabetes type 1 or 2
- BCVA ETDRS letter score in the study eye of ≥ 69 letters (approximate Snellen equivalent of 20/40 or better)
- Refraction with a spherical equivalent from -6 dpt to +5 dpt

Additionally, subpopulations as defined in Section 4.2.3 will be used for the analysis.

#### **Treatment condition:**

Runcaciguat vs. placebo

#### **Population level summary:**

The estimated difference in the proportion of responders between interventions.

#### Intercurrent events:

- Dropout due to a VTC in the study eye: *composite variable strategy* (analyze study participant as non-responder)
- Dropout ...

... before Visit 9 (week 12) composite variable strategy (analyze study participant as non-responder)

... after Visit 9 (week 12) with EoT DRSS assessment performed within 4 weeks of treatment discontinuation

while on treatment strategy (use the last available DRSS assessment (LOCF)

... after Visit 9 (week 12) with EoT DRSS assessment performed more than 4 weeks after treatment discontinuation

*while on treatment strategy* (use the last available DRSS assessment prior to treatment discontinuation (LOCF))

• Non-compliance with study intervention, defined as actual drug intake lower than 80% or higher than 120% of the planned drug intake per protocol: *principal stratum strategy* (exclusion from analysis, as an adequate imputation of response information is considered not possible)

The secondary estimand (analysis on FAS) is identical to the primary estimand (analysis on PPS) with the exception that the condition relating to compliance is not included.

Version 3.0

The other estimand (analysis on PPS) is defined below:

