## 4.2.2 Main Analytical Approach

For the primary analysis, the last observation before missing DRSS values will be carried forward (LOCF) to impute missing values if the participant dropped out after visit 9 (week 12) and the EoT DRSS assessment was performed within 4 weeks of treatment discontinuation (*while on treatment strategy*). If the last measured DRSS score already showed an improvement by  $\geq 2$  steps at the last measurement prior to the missing assessment, the participant will be considered a responder for the primary endpoint. Otherwise, the participant will be considered a non-responder. If the participant dropped out after visit 9 (week 12) and the EoT DRSS assessment was performed more than 4 weeks after treatment discontinuation the last available DRSS assessment prior to treatment discontinuation will be used (LOCF) (*while on treatment strategy*). Participants who dropped out before visit 9 (week 12), or who had a VTC in the study eye prior to the missing assessment will be considered non-responders regardless of the DRSS level (*composite variable strategy*).

Treatment groups will be runcaciguat and placebo, actually administered dose levels will not be considered for this analysis.

Primary efficacy analyses will be performed on the PPS and will include only study intervention compliant participants (*principal stratum strategy*). In addition, sensitivity analyses will be performed on the FAS. Further analyses may include a separate analysis for each runcaciguat maintenance dose level that was reached during titration (on the PPS). Participants will be analyzed according to the treatment (i.e., runcaciguat or placebo) they actually received.

The study will be analyzed using Bayesian inference with non-informative priors. PoC shall be defined as fulfillment of the following criteria:

•  $P(\pi_{ACT} - \pi_{PLC} > 0 | data) \ge 0.9$ i.e., the posterior probability that the difference between  $\pi_{ACT}$  and  $\pi_{PLC}$  is greater than 0 (clinical activity) given the data observed in the study needs to be 90% or more,

and

•  $P(\pi_{ACT} > 0.25 | data) \ge 0.5$ i.e., the posterior probability that  $\pi_{ACT}$  is greater than 0.25 (clinical relevance) given the data observed in the study needs to be 50% or more.

95% credible intervals will also be presented for  $\pi_{ACT}$  and for  $\pi_{PLC}$ 

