#### 4.3 Secondary Endpoint Analysis

#### 4.3.1 Secondary Endpoints

#### **4.3.1.1 Definition of Endpoints**

#### '≥/< x steps improvement/deterioration in DRSS (for persons)' at 48 (resp. 12, 24) Weeks of treatment (in the study eye)

These endpoints will be assessed using the same methodology described for the primary efficacy endpoint (see Section 4.2.2).

- $\geq 2$  steps improvement in DRSS' at 12, 24 Weeks of treatment in the study eye
- '< 2 steps deterioration in DRSS' at 12, 24, 48 Weeks of treatment in the study eye
- $\geq 1$  step improvement in DRSS' at 12, 24, 48 Weeks of treatment in the study eye
- $\geq 3$  step improvement in DRSS' at 12, 24, 48 Weeks of treatment in the study eye
- $\geq 3$  step improvement in DRSS for persons' at 12, 24, 48 Weeks of treatment
- '< 3 step deterioration in DRSS' at 12, 24, 48 Weeks of treatment in the study eye
- '< 3 step deterioration in DRSS for persons' at 12, 24, 48 Weeks of treatment

DRSS for persons will be derived according to Table 6-2.

Responder and non-responder definition for the endpoints above:

- For  $\geq x$  steps improvement in DRSS' endpoints
  - Participants with '≥ x steps improvement in DRSS' will be counted as *responder*
  - Participants with '< x steps improvement in DRSS' will be counted as *non-responder*
- For '< x steps deterioration in DRSS' endpoints
  - Participants with '< x steps deterioration in DRSS' will be counted as *responder*
  - Participants with '\ge x steps deterioration in DRSS' will be counted as *non-responder*

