#### Vision-threatening complications at 12, 24, 48 Weeks of treatment in the study eye

VTC will be recorded continuously during the study. Predefined timepoints for assessment are 12, 24, and 48 weeks of treatment. VTC are recorded separately for the study eye and the fellow eye. Separate assessments will be done for the study eye and across both eyes (timepoint when a VTC appears in any eye). These endpoints will be analyzed by the Kaplan-Meier-method on the PPS and in addition, as a sensitivity analyses on the FAS. Confidence intervals will be provided for probability of having a vision threatening event up to these time points. Participants dropping out from the study without a VTC will be censored at the last visit. Furthermore, if deemed necessary, the endpoint VTC in any eye (yes/no) will be analyzed using the same Bayesian analysis described for the primary efficacy endpoint (see Section 4.2.2) on the PPS.

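### For the persons-scale improvement endpoints the SAP's VTC rule covers only the study eye, so dropout after week 12 for a fellow-eye complication goes to LOCF and can be scored a response

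*SAP*

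**What the plan says.** SAP 1.1 gives the primary estimand the scope "All DRSS derived efficacy endpoints". Its only VTC intercurrent event is "Dropout due to a VTC in the study eye", handled by a composite strategy as non-response. The secondary (FAS) estimand differs only in dropping the compliance condition, so it carries the same rule. SAP 4.2.2 repeats it for participants "who had a VTC in the study eye prior to the missing assessment will be considered non-responders regardless of the DRSS level".

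Other dropouts follow the general rule. Leaving before Visit 9 is non-response. Leaving after Visit 9 means the last usable DRSS grade is carried forward.

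SAP Table 1-1 lists as a secondary endpoint an improvement of at least 3 "steps at 48 weeks of treatment on the scale for persons". SAP 4.3.1.1 lists it at weeks 12, 24 and 48 and sets the method for its whole list of DRSS endpoints: "These endpoints will be assessed using the same methodology described for the primary efficacy endpoint (see Section 4.2.2". It adds no VTC rule for the persons scale. It also says "DRSS for persons will be derived according to Table 6-2", and that table combines the levels of both eyes. On data collection, SAP 4.3.1.2 says "VTC are recorded separately for the study eye and the fellow eye".

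A VTC is PDR, any ocular neovascularization, centre-involved DME, or a BCVA loss of 10 letters or more (Protocol 8.1.2; SAP 4.3.1.1).

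**The concern.** A rule written for a one-eye endpoint has been carried to a two-eye endpoint without adaptation. On the persons scale both eyes contribute to the outcome, yet a complication that makes a participant leave counts as failure in one eye and as an ordinary dropout in the other. Centre-involved DME and visual loss are not DRSS levels, so the carried-forward grade need not reveal them.

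What is at stake is how the persons-scale result can be read. The SAP version history says this scale was adopted because it will be the Phase III primary endpoint in NPDR, to gain insight and allow comparison. A responder count that includes people who left because of a fellow-eye complication is a weaker basis for that purpose.

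**Working it through.** **1. The plan's own figure.** SAP 5 and Protocol 9.2 state at least 90% probability of PoC with 40 evaluable per arm, true rates 10% and 35%, Beta(0.5, 0.5) priors, and posterior cut-offs 0.9 (superiority) and 0.5 (active rate above 0.25). An exact sum over all responder pairs gives 90.3%. Each criterion alone gives 93.6%, and the relevance criterion needs at least 10 of 40 responders. The stated figure is reproduced. It concerns the study-eye endpoint, so this point does not touch it. The documents give no expected rate for the persons-scale endpoint.

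**2. How a VTC is scored for improvement of at least 3 persons steps.**

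| Situation | VTC in study eye | VTC in fellow eye |
|---|---|---|
| Dropout before Visit 9 | Non-responder | Non-responder (general dropout rule) |
| Dropout after Visit 9, new PDR visible in the grade used | Non-responder | Non-responder (see step 3) |
| Dropout after Visit 9, event not visible in the grade used | Non-responder | LOCF; responder if that grade is at least 3 steps better |
| Week-48 grade present | Scored on the grade | Scored on the grade |

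Only the third row differs by eye.

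**3. Can the grade itself catch the event?** I coded Table 6-2 with levels 10, 20, 35, 43, 47, 53, 61, 65 and 71+. Baseline study eye is 47 or 53, and baseline fellow eye is any level below 61.

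- Fellow eye at 61 or above later: 2 × 6 × 9 × 3 = 324 combinations. None gives an improvement of 3 steps or more, and the persons step worsens by at least 1 in all of them. Newly graded fellow-eye PDR is therefore always failure.
- Fellow eye still below 61: 2 × 6 × 9 × 6 = 648 combinations. Of these, 171 give an improvement of 3 steps or more. A VTC that DRSS does not show can therefore coexist with responder status. These are counts of possible patterns, not probabilities.

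**4. One participant.** Baseline 47/47 is step 9. At week 24 the study eye is 35 and the fellow eye 43, so the level is 43/<43, step 6, and 9 − 6 = 3. The participant then develops centre-involved DME and leaves, with no later usable grade. In the fellow eye, LOCF keeps step 6 and the participant is a responder. In the study eye, the participant is a non-responder.

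**5. Size.** Let f be the share of an arm that drops out after week 12 with a fellow-eye VTC not visible in the grade, and r the share of those who are LOCF responders. The change in the rate is f × r. Neither is in the documents. I assume f from 2% to 10%. For r I borrow the range 10% to 35% from the planning rates of the primary endpoint.

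| f | r | f × r (points) | Participants per 40 |
|---|---|---|---|
| 2% | 10% | 0.2 | 0.08 |
| 2% | 35% | 0.7 | 0.28 |
| 5% | 10% | 0.5 | 0.2 |
| 5% | 35% | 1.75 | 0.7 |
| 10% | 10% | 1.0 | 0.4 |
| 10% | 35% | 3.5 | 1.4 |

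**6. What one participant can do.** With the SAP's Bayesian method at 40 per arm, 3 against 1 responders gives a posterior probability of superiority of 0.846, and 4 against 1 gives 0.919. For 5 against 2 and 6 against 2 the values are 0.883 and 0.934. If responders are few, one reclassification can cross 0.9. These counts are illustrative, and no decision rule attaches to this endpoint.

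**The case against.** Much of the case against acting is sound. PoC is decided on the study-eye endpoint alone. VTC in any eye is analysed separately by Kaplan-Meier and, if deemed necessary, by the Bayesian method (SAP 4.3.1.2), so fellow-eye complications are not hidden. Participants who stop study drug may stay in the study (Protocol 7.1.1), which limits such dropouts. The ocular exclusions in Protocol 5.2 mostly concern the study eye, so a fellow eye may enter with disease already present, and a bare either-eye rule would be too blunt. None of this explains why the same dropout event should be scored differently by eye on a two-eye scale.

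A reader might infer two stronger things that the documents do not support.

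- *A fellow-eye complication never counts as failure.* The first two rows of the table in step 2 show otherwise.
- *The study-eye rule lets local treatment of a fellow eye pass as drug effect.* Protocol 8.1.2 allows anti-VEGF for centre-involved DME, and Protocol 4.2 reports DRSS improvement with such injections, so the worry is reasonable. But it concerns participants whose later grade is present, and there the SAP has no VTC override for either eye. Writing either eye into the dropout rule would not change it. An estimate such as 15% treated × 25% improving one step × 60% falling far enough = 2.25% uses inputs that are all assumed. It also overcounts. If the study eye is strictly worse and improves by one step, the best possible change is 8 to 6 (from 47/<47) or 10 to 8 (from 53/<53), which is 2 steps.

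**Conclusion.** The point holds in limited form. For the improvement endpoints on the persons scale, a fellow-eye VTC is not itself treated as failure. The gap is dropout after week 12 following a fellow-eye event that the carried-forward grade does not show. On the assumed ranges it changes the persons-scale rate by 0.2 to 3.5 points, or 0.1 to 1.4 participants per 40.

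A reader might also infer a bias in favour of runcaciguat. The documents give no fellow-eye VTC rate by arm, so neither its direction nor its existence can be shown. The primary endpoint, the PoC decision and the 90% figure stand as they are. The correction is still worth making, because the inconsistency is explicit, the repair is simple, and the SAP gives this scale a role in planning Phase III.

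**What to change.** For the endpoints of at least 3 steps improvement on the persons scale, replace the study-eye VTC condition by a VTC in either eye, new since baseline. Make the change in the dropout and missing-assessment rule of SAP 1.1 and 4.2.2, or add a persons-scale rule in SAP 4.3.1. It should apply to both the PPS and FAS estimands. Leave the study-eye endpoints unchanged.

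The cost is SAP wording and a slightly lower persons-scale response rate. VTC are already recorded by eye. The SAP would need to say how a fellow-eye condition present at baseline is told apart from a new one; the scheduled screening and baseline eye examinations are bilateral.

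Optionally, add a sensitivity analysis that counts a VTC in either eye followed by local retinal treatment as non-response even when a later grade is present. This is a different estimand and should not replace the main analysis. Before adding it, confirm that treatment is captured by eye and includes laser, since Protocol 6.8 lists medication fields only.
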